**Analysis of Activity 5:**

We will extract structured data from the six health systems participating in SIMPRO. These data include ePROs, demographics, diagnoses, treatment plans, medications, and inpatient and outpatient encounters. We will develop risk prediction models for adverse events, especially including, but not limited to hospitalizations and emergency department visits. Planned hospitalizations will be identified and excluded based on A) admissions within 24 hours of the

triggering surgery among surgical patients; and B) admissions associated with curative-intent surgeries among medical oncology patients with early-stage cancers. For models incorporating ePROs as predictors, the analytic cohort will include patients who completed at least one survey. For models excluding ePROs as predictors, the analytic cohort will include all patients in the database.

Data from at least one health system will be removed from the dataset to serve as an external test set. Among the remaining health systems, the population will be split at the patient level with 70% randomly assigned to a training cohort, 15% assigned a validation cohort and 15% assigned to an internal test set. To account for differences in clinical practice and demographics across health systems, randomization will be stratified by system. The same cohorts will be used to train and test all algorithms.

To determine the optimal machine learning model, we will evaluate multiple types of architectures, including logistic regression, random forests, gradient boosted machines, extreme gradient boosting, neural networks, and ensemble models. Hyperparameters will be tuned using the validation cohort and models iteratively trained until a final candidate model is identified. This model will then be evaluated on the held-out internal test set and the external test cohort, after which no further model training will be performed. These steps will be performed separately for the ePRO-responding cohort and the total cohort.

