4.1. Outcomes and summary measures

- **Table 5** shows the outcomes for Aim 2 and the summary measure to quantify the treatment effect magnitude for each outcome. The treatment effect magnitude on each outcome will be reported in both absolute and relative terms. terms (CONSORT Checklist Item 17b).⁷
- The primary outcome for Aim 2 is Emergency Department Treat/Release (EDTR) event occurrence status at 30-day post-chemotherapy start date (for MO) or at 30-day post-surgical discharge date (for Surg). The summary measure of this outcome is the proportion of the event occurrence at Day 30.
- Day 1 for each outcome is defined as the date of the initiation of chemotherapy for MO or the date of discharge from hospital (for Surg). However, events occurring on the first day of chemotherapy infusion or the day of discharge after surgery will be not counted as an “event,” because they could not have been impacted by the eSym program. By this definition, there will be no event at Day 1.

Table 5: Outcomes of Aim 2a

Outcome	Type of outcome	Summary measure for each group	Estimand (summary measure for between-group difference)	Cohort
Emergency Department Treat/Release (EDTR) event occurrence status at Day 30 [primary]	Binary	Proportion	Absolute Difference (AD) and Odds Ratio (OR)	MO and Surg
EDTR event occurrence status at Day 90	Binary	Proportion	AD and OR	MO and Surg
Number of the EDTR event occurrences during 180-day of follow-up	Count in a given follow-up period	Incidence rate on (0, 180d)	Incident Rate Difference (IRD) and Incidence Rate Ratio (IRR)	MO and Surg
Number of the EDTR event occurrences during 365-day of follow-up	Count in a given follow-up period	Incidence Rate on (0, 365d)	IRD and IRR	MO and Surg
ED-hospitalization event occurrence status at Day 30	Binary	Proportion	AD and OR	MO and Surg
ED-hospitalization event occurrence status at Day 90	Binary	Proportion	AD and OR	MO and Surg

Statistical Analysis Plan for Protocol Activity 4: Pragmatic Stepped-Wedge Cluster Randomized Trial
SIMPRO Research Center: Integration and Implementation of PROs for Symptom Management in Oncology Practice

Number of the ED-hospitalization event occurrences during 180-day of follow-up	Count in a given follow-up period	Incidence rate on (0, 180d)	IRD and IRR	MO and Surg
Number of the ED-hospitalization event occurrences during 365-day of follow-up	Count in a given follow-up period	Incidence Rate on (0, 365d)	IRD and IRR	MO and Surg

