Occurrence of 1 st chemotherapy discontinuation during one-year follow-up period	Time to event	Incidence Rate on (0, 365d)	IRD and IRR	All MO
Occurrence of 1 st admission during one-year follow-up period	Time to event	Incidence Rate on (0, 365d)	IRD and IRR	All MO
Occurrence of 1 st re-operation during one-year follow-up period	Time to event	Incidence Rate on (0, 365d)	IRD and IRR	All Surg
Occurrence of 1 st re-admission during one-year follow-up period	Time to event	Incidence Rate on (0, 365d)	IRD and IRR	All Surg
Death during one-year follow-up period	Time to event	Incidence Rate on (0, 365d)	IRD and IRR	MO and Surg
Composite of EDTR, Hospitalization, and Death event occurrence status at Day 30	Binary	Proportion	Absolute Difference (AD) and Odds Ratio (OR)	MO and Surg
Death during 30-day post-chemotherapy start date (for MO) or at 30-day post-surgical discharge date (for Surg)	Time to event	Incidence Rate on (0, 30d)	IRD and IRR	MO and Surg
Notes:				

 The Day 1 is defined the chemotherapy start date for MO and the discharge date for Surgery. All outcomes are defined in relation to the date of discharge from hospital (for Surg) or the initiation date of a new chemotherapy regimen (for MO). Note that events occurring on the first day of chemotherapy or the day of discharge after surgery will be excluded, because they could not have been impacted by the eSym program. 				

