- Death is a competing event for EDTR and Hospitalization. In the primary analyses for EDTR and Admission, those who die without EDTR or Hospitalization will not be excluded from the analyses but included in the denominator when calculating the EDTR rate and Admission rate. Caution should be exercised in interpreting the intervention effect on these non-fatal outcomes. Because those who die before these non-fatal events will never experience it, the intervention effect on these non-fatal events will be biased in favor of either the control or intervention group where more deaths are observed. Therefore, when assessing the effectiveness of the intervention, we will also consider its impact on reducing death (a secondary outcome; see Table 5).
- As a sensitivity analysis for concluding the effectiveness of the intervention, we will analyze the composite of EDTR, Hospitalization, or Death event occurrence status at Day 30 (a secondary outcome; see Table 5), which is not subject to the competing risk problems.

Handling of potentially differentiable follow-up duration across episodes:

- While the planned follow-up duration for each episode is one-year, the actual follow-up durations of some episodes will be shorter than one year due to the occurrence of another trigger event or lost-to-follow-up during the one-year follow-up. Thus, the follow-up duration will be different across the episodes.
- For binary outcomes (i.e., the event status yes/no), the length of follow-up time will not be considered in the analysis. We expect that this will not affect the analysis of the primary endpoint (EDTR at Day 30) because we expect that we will have at least 30 days of follow-up for all episodes. The potential reason of censoring of follow-up is the occurrence of another trigger event during the follow-up time. It is unlikely for a patient to have another trigger event within 30 days after the previous trigger event.
- For count data, we will take the length of the follow-up period for each episode into account. Specifically, we will use Poisson regression models, where the logarithm of follow-up duration of each episode will be included as offset in the models.

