4.8. Table shell for presenting the primary analysis results

MO and Surgery Combined						
	Number of Observed Events (%)		Odds Ratio		Absolute Difference	
Outcomes	Intervention (#patients=XX) (#episodes = XX)	Control (#patients=XX) (#episodes = XX)	Estimate (0.95 CI)	p-value	Estimate (0.95 CI)	p-value
EDTR Day 30	XX (XX%)	XX (XX%)	X.XX (X.XX to X.XX)	X.XXX	X.XX (X.XX to X.XX)	X.XXX
EDTR Day 90	XX (XX%)	XX (XX%)	X.XX (X.XX to X.XX)	X.XXX	X.XX (X.XX to X.XX)	X.XXX
Admission Day 30	XX (XX%)	XX (XX%)	X.XX (X.XX to X.XX)	X.XXX	X.XX (X.XX to X.XX)	X.XXX
Admission Day 90	XX (XX%)	XX (XX%)	X.XX (X.XX to X.XX)	X.XXX	X.XX (X.XX to X.XX)	X.XXX
MO Only						
	Number of Observed Events (%)		Odds Ratio		Absolute Difference	
Outcomes	Intervention (#patients=XX) (#episodes = XX)	Control (#patients=XX) (#episodes = XX)	Estimate (0.95 CI)	p-value	Estimate (0.95 CI)	p-value
EDTR Day 30	XX (XX%)	XX (XX%)	X.XX (X.XX to X.XX)	X.XXX	X.XX (X.XX to X.XX)	X.XXX
EDTR Day 90	XX (XX%)	XX (XX%)	X.XX (X.XX to X.XX)	X.XXX	X.XX (X.XX to X.XX)	X.XXX
Admission Day 30	XX (XX%)	XX (XX%)	X.XX (X.XX to X.XX)	X.XXX	X.XX (X.XX to X.XX)	X.XXX
Admission Day 90	XX (XX%)	XX (XX%)	X.XX (X.XX to X.XX)	X.XXX	X.XX (X.XX to X.XX)	X.XXX
Surgery Only						
	Number of Observed Events (%)		Odds Ratio		Absolute Difference	
Outcomes	Intervention (#patients = XX) (#episodes = XX)	Control (#patients=XX) (#episodes = XX)	Estimate (0.95 CI)	p-value	Estimate (0.95 CI)	p-value
EDTR Day 30	XX (XX%)	XX (XX%)	X.XX (X.XX to X.XX)	X.XXX	X.XX (X.XX to X.XX)	X.XXX
EDTR Day 90	XX (XX%)	XX (XX%)	X.XX (X.XX to X.XX)	X.XXX	X.XX (X.XX to X.XX)	X.XXX
Admission Day 30	XX (XX%)	XX (XX%)	X.XX (X.XX to X.XX)	X.XXX	X.XX (X.XX to X.XX)	X.XXX
Admission Day 90	XX (XX%)	XX (XX%)	X.XX (X.XX to X.XX)	X.XXX	X.XX (X.XX to X.XX)	X.XXX
Factors used for the adjustment: XXX, XXX, XXX, XXX						

5. Analysis for Aim 2b: Impact on initiation of adjuvant chemotherapy and chemotherapy duration.

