Boston, MA 02215
Email Address: [contact]
[contact]

CO-STUDY CHAIRS:

[name] [name]
Chair, Department of Medicine
Memorial Sloan Kettering Cancer Center
New York City, NY 10065

[name] MD
Director, Thoracic Oncology Research Group
Baptist Memorial Hospital
Covington, Tennessee 38019

[name] MD
Chair, Department of Surgery
Dartmouth College
Lebanon, NH 03756

STUDY STATISTICIAN:

[name]
Dana-Farber Cancer Institute
Boston, MA 02215

FUNDING:

National Cancer Institute, UMICA233080.

SIGNATURE PAGE

Protocol Title: SIMPRO Research Center: Integration and Implementation of PROs for Symptom Management in Oncology Practice.

Sponsor Protocol Number: DF/HCC IRB #18-986R/18-734

sIRB Protocol Number: WIRB Tracking #20182593; Study #1248093

SAP Version: Addendum to Version 2.0

Date: June 12, 2024

[name], MPH
Study Chair, Coordinating Center PI

Date

[name], MPH
Co-Chair, Co-PI

Date

[name]
Co-Chair, Co-PI

Date

[name]
Co-Chair, Co-PI

Date

[name]
Study Statistician

Date

Introduction

This addendum outlines modifications to the Statistical Analysis Plan (SAP) version 2.0 (January 9, 2024) for the pragmatic stepped-wedge cluster randomized trial at SIMPRO Research Center due to challenges encountered in the original analysis plan.

In this study, follow-up for clinical outcomes for each patient starts from the occurrence of a trigger event (i.e., initiation of a new chemotherapy for Medical Oncology and discharge after receiving a qualifying surgical procedure for Surgery). Therefore, we potentially have more than one data point (i.e., episode) from one subject in this study.

The primary analysis has been adjusted from including all episodes observed from each patient during the study period (see Pages 12 of the SAP ver. 2.0) to including only the first episode observed from each patient. Accordingly, the primary analysis has been changed from including subjects as random effects in generalized linear mixed effects models to take account of within-subject correlation (see Page 17 on the SAP ver. 2.0) to using generalized linear models because the analysis data will not involve within-subject correlation.

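### Table 5's one-year first-admission outcome for medical oncology has no planned-admission exclusion, and the section 4.8 shell does not match Table 5 on the Day 30/90 hospital outcome

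*SAP*

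**What the plan says.** **Admission outcomes.** SAP section 4.1, Table 5, has "Occurrence of 1 st admission during one-year follow-up period" for all MO patients and "Occurrence of 1 st re-admission during one-year follow-up period" for all surgical patients, each summarised by the incidence rate difference and ratio. Neither is limited by route of entry or by planned status. The only events that Table 5 removes are those on Day 1 (the first chemotherapy day, or the day of discharge), on the ground that eSyM could not have influenced them.

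**ED-hospitalization outcomes.** Table 5 also has "ED-hospitalization event occurrence status at Day 30", the same outcome at Day 90, and counts over 180 and 365 days.

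**Composite.** Table 5 lists "Composite of EDTR, Hospitalization, and Death event occurrence status at Day 30". Section 4.4 gives it a role: "As a sensitivity analysis for concluding the effectiveness of the intervention, we will analyze the composite of EDTR, Hospitalization, or Death". Neither place says which hospital stays qualify.

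**Shell.** All three panels of section 4.8 have rows for "Admission Day 30" and for Day 90, and none for ED-hospitalization. The competing-risk text in section 4.4 uses hospitalization and admission interchangeably.

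**Activity 5.** Protocol section 10 excludes planned hospitalizations in two parts. Part A covers admissions within 24 hours of the triggering surgery. Part B covers "admissions associated with curative-intent surgeries among medical oncology patients with early-stage cancers". Activity 5 uses all the patient-level data of Activity 4.

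**Episode rule.** Under SAP section 4.2, a new qualifying trigger (Event B) during follow-up ends the earlier episode, and data collected after Event B belong to the new one. That section describes the surgical trigger as a qualifying procedure. The Addendum's introduction describes it as "discharge after receiving a qualifying surgical procedure for Surgery".

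**The concern.** A scheduled resection after neoadjuvant chemotherapy is part of the treatment plan and not a failure of symptom control. If its admission counts as the first admission of the MO episode, an outcome meant to reflect acute care includes stays that eSyM is not designed to prevent. The SAP's own reason for dropping Day-1 events applies to such stays too. The protocol team treated them as identifiable and excluded them in Activity 5. The SAP and its Addendum neither adopt that rule nor explain why it is left out.

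The expected result is an MO admission effect pulled towards no difference. If eSyM helped more patients complete treatment and reach surgery, that benefit would itself add events.

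The labels raise a separate problem. The shell is where the results will appear, and it names an outcome at Day 30 and Day 90 that Table 5 does not define. The Addendum reports convergence problems with the planned models, so models have already been fitted. An open label now leaves a choice of outcome after data access.

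**Working it through.** The plan gives no rate, effect size or power for the admission outcomes or the composite, so there is no figure to reproduce. The check has three parts.

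**1. Does any rule remove the resection admission from the MO episode?** Take a patient who starts neoadjuvant chemotherapy (Event A) and is later admitted for a qualifying resection (Event B).

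| Event B dated at | Admission relative to Event B | Moved to the surgical episode? |
|---|---|---|
| Discharge (Addendum) | Before | No |
| Procedure (SAP 4.2) | Same day or earlier | Not after Event B, so no on the literal wording |
| Admission | Same day | Not settled by the text |

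Only data after Event B move, so on the literal wording nothing takes the admission out of the MO episode. The Addendum's restriction of the primary analysis to first episodes does not change this: if the neoadjuvant course is the patient's first episode, that is the one analysed. A planned stay for a non-qualifying procedure does not trigger Event B at all.

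**2. Are admission and ED-hospitalization the same outcome here?** Protocol section 12 (Activity 4c) lists hospital admission rates separately from ED visits, which it splits into those ending in admission and those ending in discharge. Table 5 also keeps ED-hospitalization and first admission on separate rows. The shell's label therefore cannot be assumed to mean the Table 5 outcome.

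**3. How large could the dilution be?** Let s be the planned share of first MO admissions and r the IRR for unplanned admissions. Both are assumptions. With planned stays unaffected by eSyM, approximately:

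IRR (all admissions) = r(1 - s) + s

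- r = 0.80, s = 0.10: 0.72 + 0.10 = 0.82
- r = 0.80, s = 0.30: 0.56 + 0.30 = 0.86

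If eSyM also raised planned surgery by 10% (a further assumption):

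- s = 0.10: 0.72 + 1.1 × 0.10 = 0.83
- s = 0.30: 0.56 + 1.1 × 0.30 = 0.89, which loses (0.89 - 0.80)/(1 - 0.80) = 45% of the effect

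Events needed for 80% power (Schoenfeld's formula, two-sided 0.05, 1:1, clustering ignored) rise from 631 at 0.80 to 798 at 0.82 and 1,381 at 0.86. These counts only show how the burden scales; they are not a power calculation for this trial.

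**Sign reversal.** At s = 0.30, an IRR of 1.0 needs 0.56 + 0.30m = 1, so m = 1.47, a 47% rise in planned surgery. With a 10% rise, 0.80 + 0.30s = 1 needs s = 0.67, more than twice the upper share assumed here.

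**The case against.** The SAP is silent on planned admissions; it does not say that they count. An all-cause first admission is a defensible outcome in a pragmatic trial, and the protocol's PICOTS table lists hospitalizations without qualification. Activity 5 builds prediction models, so its exclusion need not bind an effectiveness comparison. Section 4.2 makes a qualifying procedure a trigger, which could be read as giving the whole surgical stay to the new episode. Excluding stays by intent and stage also brings in misclassification. These arguments are reasons to state the choice. They do not supply the missing definition or the date of Event B.

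Several stronger readings are tempting but not supported:

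- **All of Aim 2a's hospital outcomes are contaminated.** The four ED-hospitalization outcomes require entry through the ED, and two of them already count acute hospital use over 180 and 365 days.
- **The composite counts planned stays.** Its hospital component is undefined and may mean ED-hospitalization. Section 4.4 also expects a second trigger within 30 days to be unlikely, so few qualifying resections would fall in the window.
- **The Activity 5 rule would make surgical re-admission unplanned.** Part A concerns the 24 hours around the triggering surgery, while surgical follow-up begins at discharge with Day 1 excluded. Part B covers MO patients only. Applied to re-admission, the rule removes essentially nothing.
- **The shell shows a wider outcome was intended.** Section 4.4 mixes the terms, so loose wording is equally possible.

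**Conclusion.** The point stands for one secondary outcome and for a set of labels. MO first admission over one year is undefined as to planned stays, and on a literal reading it includes planned resection admissions that the protocol excludes from the same data elsewhere. With an assumed planned share of 10-30% and an assumed unplanned IRR of 0.80, the observed IRR would be about 0.82-0.86. That is dilution; a reader might infer that the sign could reverse, but none of the values assumed here takes the IRR above 0.89. Whether the resection admission counts depends on how Event B is dated for surgery, which the SAP does not say.

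The shell and section 4.4 need to match Table 5, and the composite needs a definition because section 4.4 relies on it when concluding on effectiveness. The primary outcome (EDTR at Day 30), its power calculation and the ED-hospitalization outcomes as Table 5 defines them are untouched.

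**What to change.** 1. **MO first admission (Table 5):** analyse it excluding the planned curative-intent surgical admissions identified by part B of the Activity 5 rule, and report the all-admission version as supportive. Label it by what it excludes, since other elective stays remain.
2. **Event B (section 4.2):** state whether the surgical trigger is dated at admission, procedure or discharge, and which episode holds the surgical stay.
3. **Surgical first re-admission:** do not call it unplanned on the strength of the Activity 5 rule. Keep it as all-cause, or give it its own planned-stay definition.
4. **Composite:** specify the hospital component, for example ED-hospitalization to match Table 5.
5. **Labels:** replace admission at Day 30/90 in the section 4.8 shell, and admission in section 4.4, with the Table 5 outcome ED-hospitalization.
6. **Timing:** date the clarification relative to data access.

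The cost is SAP wording and reuse of a flag that Activity 5 already requires. No new data are needed: protocol section 12 (Activity 4c) already collects procedure codes, dates and goals, staging and treatment intention. The downside is fewer events and some misclassification of planned and unplanned stays from EHR codes, which is why the all-admission version should be reported alongside.

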4.2. General Analytic Approach

[figure not shown]
Medical Oncology and Surgery:

- The primary analysis will include data from both medical oncology (MO) and surgery (Surg) and estimate a common effect of the intervention in MO and SO. An indicator variable (MO vs. Surg), interaction between MO/Surg and Site, and interaction between MO/Surg and background time trend will be included as covariates for adjustment in multilevel generalized linear regression models.
- As a secondary analysis, for each outcome, the heterogeneity of the intervention effect by MO/Surg will also be assessed by the test for interaction between the intervention (eSym yes/no) and MO/surg using multilevel generalized linear regression models. In this analysis, the interaction between the intervention and MO/Surg will be added to the model for the primary analysis.
- As another secondary analysis, we will analyze the data from MO and Surg separately and estimate the intervention effect for each outcome. Note that this analysis is similar to the aforementioned secondary analysis including the interaction between the intervention and MO/Surg. While the aforementioned secondary analysis assumes common effects of patients' characteristics (such as age, race, gender and so on) across MO and Surg, this analysis consider these are possibly different between MO and Surg.

Determination of the intervention and length of follow-up for each episode:

- The presence /absence of the intervention (eSym+ vs. eSym-) is determined in a cross-sectional way at the time of the occurrence of the trigger event
- The follow-up period for each episode is one year from the chemotherapy start date (**MO**) and the date of discharge (**Surg**)

- The intervention determined at the trigger event will never change during the one-year of follow-up period unless another trigger event occurs (see Figure below)

- Some subjects may experience more than one trigger event (i.e., a new chemotherapy treatment plan for **MO** and a qualifying procedure for **Surg**) during the study. Thus, potentially, multiple data points/episodes will be collected from one patient.
- The primary analysis will include all these episodes other than the following episodes:
 - MO episode where its trigger event occurred after the patient was exposed to eSyM Surg, but before eSyM MO was rolled out in the patient's site.
 - Surg episode where its trigger event occurred after the patient experienced eSyM MO, but before eSyM Surg was rolled out in the patient's site.
 - For example, the 4th episode in the Figure (below) was before go-live of MO in this site and thus this episode is considered eSyM control data(eSyM-). While this patient did not experience the eSyM MO intervention at that time, this patient already experienced the eSyM Surg intervention (eSyM+) (see the 3rd episode in the figure). Therefore, we do not include the 4th episode as eSyM control (eSyM-) data but exclude it from the primary analysis.

[figure not shown]

- As sensitivity analyses, we will perform the analyses using the data consisting of only the first episode from each subject.

Occurrence of another trigger event during the follow-up of an episode:

- If another trigger event (Event B) occurs during the one-year follow-up period of a trigger event (Event A), the data collected after Event B will be included in the aggregation as data of the episode triggered by Event B, not by Event A (Figure below)

Example

Analysis Populations:

All eligible subjects accrued in this study will be included in the primary analysis. To investigate the impact of patient's engagement with eSyM on clinical outcomes, two additional analysis populations will be considered for secondary and exploratory analyses.

To this end, we consider 3 total groups for analysis:

- Group A: episodes where subjects engaged* with eSyM among the eligible episodes of eligible subjects observed in the eSyM intervention (eSyM+) period.
- Group B: episodes where subjects did not engage with eSyM among the eligible episodes of eligible subjects observed in eSyM+.
- Group C: eligible episodes of eligible subjects observed in the eSyM control (eSyM-) period

* Definition of episodes where patient engaged with eSyM: episodes where patient reports ePRO through eSyM at least once during the follow-up

Table 6 shows the details of each analysis population.

Table 6: Analysis Populations and Objectives

Analysis Population	Comparison	Objective	Notes
1) A+B+C	(A+B) vs. C (Primary analysis)	Estimating the effect of eSyM exposure in a future population similar to the entire study population	Exposed to eSyM vs. Unexposed to eSyM regardless of engagement with the exposure (Effectiveness) Clinical outcome data from all groups will be included in the analysis on the basis of the Intention-to-treat principle.
2) A+C*	A vs. C (Pre-specified Secondary)	Estimating the effect of eSyM exposure in a future population that consists of patients who will engage with eSyM upon exposure.	Exposed to eSyM vs. Unexposed to eSyM conditional on engagement with eSyM (Efficacy) C* is a subset selected from C, so that the case-mix matches A (i.e., Engagement with eSyM). A and B are used to build the propensity score to select C*.
3) A+B	A vs. B (exploratory)	Estimating the effect of eSyM engagement in a future population similar to the study population if everyone engages, under the assumption that everyone in that population engages with eSyM upon exposure.	Engagement with eSyM vs. Unengagement with eSyM, conditioning on everyone being exposed to eSyM Propensity score weighting will be used to adjust for case-mix.
Data collected before go-live (eSyM-)		Data collected after go-live (eSyM+)	
C. Episodes under the control condition		A. Episodes under the intervention condition, where patient engaged with eSyM B. Episodes under the intervention condition, where patient did not engage with eSyM	

- 1) The primary analysis population consists of all eligible episodes under the intervention condition (A+B) (i.e., eSyM exposed) and all eligible episodes under the control condition (C) (i.e., eSyM unexposed).
- 2) The secondary analysis population consists of the episodes where patients engaged with eSyM (A) and the matched episodes during the pre-intervention period (C*). C* is a subset of C. In this analysis, we are interested in estimating the intervention effect among a subgroup of patients who will engage with eSyM if exposed. First, for MO and Surg, a propensity score model (a logistic regression model) to predict engagement with eSyM will be derived using the data from A and B. Next, for each subject in A and C, the predicted probability of engagement will be calculated using the derived propensity score model. The pre-specified variables used for the propensity score models are listed in **Table 7**. For each intervention episode in A, one control episode in C will then be matched, without replacement, based on their predicted probabilities of engagement, using the nearest neighbor matching method stratified by site. The matched dataset is then run through the same outcome model as the primary comparison.
- 3) As exploratory analyses, we will compare A vs. B. Under the condition that the hospitals have switched on the eSyM system (i.e., everybody is exposed to the eSyM system), we are interested in estimating the effect of the eSyM engagement on the outcomes under the assumption that everyone engages with eSyM, compared to the case where no one engaged with eSyM in spite of eSyM exposure. A propensity score weighting will be used to adjust for the case-mix between engagement with eSyM and non-engagmenet with eSyM. We will build a propensity score model for MO and Surg, separately, using the data from A and B. The pre-specified variables used for the propensity score models are listed in **Table 7**. No outcome model will be involved in this analysis.

Table 7: Pre-specified variables included in the propensity score models

Variable	2) A vs. C*	3) A vs. B	Note
Goal of Chemotherapy (MO with curative goal, MO with palliative goal, Others)	X	X	Only the models for MO
Calendar Time (Secular trends) [continuous with natural cubic spline]		X	
Site (Treating Facility) (DFCI, MMC, DHMC, LCI, BAPT, WVU)	X	X	
Age (year) (fractional polynomials)	X	X	
Sex (male vs. female)	X	X	
Race/Ethnicity (white/non-Hispanic, black/non-Hispanic, Hispanic, Other/Unknown)	X	X	
Employment (Employed, disabled, retired, other)	X	X	
Marital status (married vs. not married)	X	X	
Rurality based on zip code (large metro, small metro, suburban, rural)	X	X	
Insurance type (Medicare only, Medicare and Medicaid, Medicaid only, Private, Other)	X	X	
Cancer type (GI, Gyn, Thoracic)	X	X	
Socio-economic status (quintiles by the zip code-based poverty level)	X	X	
Co-morbidity (Charlson comorbidity index from encounter diagnoses in the 12 months before the first eligibility date) (0, 1, 2+)	X	X	

